2.3.2 Secondary objectives

- 1. To assess participants response (treatment efficacy) to varying dose concentrations, dose frequency, length of treatment, and formulation of *Artemisia afra* treatment.
- 2. To identify the most acceptable dose concentration, dose frequency, length of treatment, and formulation (flavor) of Artemisia treatment.
- 3. To assess the safety (ASE) of *Artemisia afra* treatment in participants by dose concentration, dose frequency, length of treatment, and formulation. As a commonly used tea, no toxicity is expected.
- 4. To assess variability of plasmodium test predictive values between mRDT, rtPCR, and direct blood smear observation in asymptomatic persons.

Treatment outcomes

Major outcome

• Decrease in parasite load over time.

Secondary outcomes

- Decrease in gametocyte load in carriers with Artemisia afra tea by dose concentration, dose frequency, length of treatment, and formulation.
- Acceptability (adherence and completion) of *Artemisia afra* treatment by dose concentration, dose frequency, length of treatment, and formulation (flavor).

- Safety (SAEs) of *Artemisia afra* treatment in participants by dose concentration, dose frequency length of treatment, and treatment formulation.
- Absolute increase in Cycle threshold (Ct >20).
- Likelihood and variability in the rate of reservoir elimination with treatment, compliance/ acceptability, and occurrence of side effects /adverse events in different treatment arms.

Treatment endpoints

Primary endpoints

• Proportion of people with decreased gametocyte load after treatment with *Artemisia afra* tea on Day 35 from baseline.

Secondary endpoints

- Level of decrease in gametocyte load (rt-PCR Ct) in the different treatment arms at D7, D14, D28, and D35 from baseline (activity level and optimal dosage schedule).
- Level of decrease in gametocyte load the various treatment arms (rt-PCR Ct) by gender, age, and trial entry parasite load, at D7, D14, D28, and D35 from baseline.
- Absolute increase in Cycle threshold (Ct >20) in various treatment arms at D7, D14, D28, and D35 from baseline.
- Proportion of people in the various treatment arms who respect and complete the prescribed treatment dosages (accepted dosage schedule and drug formulation).
- Proportion of persons on the various arms of treatment who develop clinical symptoms at D7, D14,
 D28, and D35 from baseline.

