Randomization: Prior to treatment, eligible participants will be randomly assigned into the 8 study arms. The randomization method will be a permuted block randomization, with a block size of either 14 or 28 at random, and with a two-to-one allocation ratio for each active arm against two different control arms (2:2:2:2:2:1:1).

Blinding: The participants in the intervention arms will be aware of their assignment to an intervention group but unaware of the treatment assigned to them. The site staff (investigators or observers) will be

aware of assignments to one control arm (regular tea group), but unaware of assignments in the other treatment arms.

Visits/assessment schedules: A total of five study visits will be effected, being one baseline visit on Day 0, and four follow-up visits on Day 7, 14, 28 and 35, from baseline. During the baseline visit plasmodium tests targeting specific parts of the gametocyte genes will be done to determine the participants' initial (baseline) parasite load, and during subsequent visits, follow up control tests (rtPCR and blood smear) will be done, and the gametocyte load recorded, alongside assessments for clinical symptoms and adverse sides effects (if any).

Endpoints The efficacy of each of the treatment dosage schedule will be evaluated on day 7,14,28 and 35 from baseline, based on response to treatment or reservoir elimination rate. Response to treatment will be indicated by an absolute increase in Cycle threshold (Ct >20), or a negative rt-PCR tests results (Ct >40). If the patient misses the follow-up visit, compliance will be noted in the completion worksheet (filled out at end of study) and the parasite load and adverse side effects noted during the last visit considered. No severe side adverse effects are expected from the treatment but since toxicity is always a concern in clinical trials involving humans, participants will be observed for any severe ASEs and withdrawal noted throughout the study duration.

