4. STUDY POPULATION

The study will be conducted at the University of Buea in Cameroon, and the University of Rwanda. All students and staff members of the University will be invited to participate. In the University of Buea, there are about 12,000 students and 973 staff members (500 teachers and 473 administrative /supporting staff. The University of Rwanda (UR) has about 30,445 students and 2,266 staff members (1450 teachers and 816 administrative /supporting). All students and staff members of the University will be invited to participate in the study. Participants will be included in the study if in good health as judged by physical examination and medical history, and if they meet all specified eligibility criteria.

Table 3: Inclusion and exclusion criteria.

Inc	Inclusion criteria for trial allocation groups		Exclusion criteria for trial allocation groups	
1.	Be student or worker of a participating	1. To have a known hypersensitivity to any ingredients		
	University.		of the tea.	
2.	Be 18 years and above, and in good general	2.	Currently taking a malaria drug for prevention or	
	health condition.		treatment.	
3.	Have a device (phone, tablet, etc) that will	3.	To have participated in another malaria drug trial or	
	support remote visits.		device in the last 14days.	
4.	Sign written informed consent form.	4.	To have a history or presence of clinically significant	
5.	Screened positive for malaria (RDT + and		medical, psychiatric, or emotional condition.	
	qPCR +) but asymptomatic.	5.	Reported diabetic.	

5-STUDY PROCEDURES

5.1 General considerations: The study will be conducted in accordance with the ethical principles for medical research involving humans in the World medical associations declaration of Helsinki (36). The study will be initiated only after approvals from relevant authorities, ethical and institutional review boards have been obtained. Freely given and written informed consent must be obtained from each participant prior to participation in the study.

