5.7 Laboratory tests

Before randomization during the baseline visit (D0), blood samples will be collected from each participant and examined for the presence of parasites (Gametocytes) using Malaria rapid diagnostic test kit (BIOCREDIT Malaria Ag P.f/Pan RDT). RDT positive samples will be re-examined with qPCR (quantitative polymerase chain reaction) and direct microscopy for confirmation. The qCPR will be repeated for negative samples and participants excluded if still negative. All qPCR positive samples will be further analyzed with rt PCR (real time polymerase chain reaction), for parasite quantification and specific stage identification, targeting specific parts of the gametocyte genes.

- a. *BIOCREDIT Malaria Ag P.f/Pan RDT*: This is a three-band RDT that detects HRP2 and pan-pLDH antigens which will detect the presence of P. falciparum (HRP2) and of another specie (pan-pLDH). Results will be interpreted as Negative (band absent) Mildly positive (faint band appearance) strongly positive (conspicuous band appearance).
- b. *Direct microscopy*: Direct Microscopic identification of parasites will be performed using thin and thick blood films stained with Giemsa and quantified as number of parasites per milliliter of blood.
- c. *rtPCR*): The parasite load will be measured based on the number of rtPCR cycle thresholds (Ct) (which is an inverse proportion of the parasite load) and classified as absolute increase in Cycle threshold (Ct >20), or negative rt-PCR tests results (Ct >40).
- d. *Blood sample schedule*: Five blood samples (approximately 1mL each) will be collected at Visit 1 (Day 0), Visit 2 (Day 7), Visit 3 (Day 14), Visit 4 (day 28), and visit 5 (day 35). After conducting the 3 or 4 tests at visit 1, only the rtPCR test and blood smear microscopy will be done during subsequent evaluations.

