8. STATISTICAL CONSIDERATIONS AND ANALYSIS PLAN

8.1 Sample size calculations

As a pilot study, we will recruit 8 asymptomatic plasmodium carriers per study-arm in the 6 trial arms and 4 participants per arm in the 2 control (placebo) arms. Therefore 56 positive participants will be enrolled per site, making 112 participants in the whole study. To reach the required number of 56 gametocyte carriers, 635 persons will be RDT tested in Buea (south west region) where the expected positive RDT was 9.8% in Demographic health survey (DHS) 2018 (34) and drop-out rate was set at 10%. In Huye (South region) where the expected positive RDT was 6.9% in Malaria indicator survey (MIS) 2017 (35) and drop-out rate was set at 10%, 432 persons will be RDT tested to reach the required number of 56 gametocyte carriers.

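### The Ct response rule has two readings and neither works when baseline Ct is above 20; the primary endpoint is a third rule with no minimum change

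*Protocol*

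**What the plan says.** Section 3 (Endpoints) evaluates each dosage schedule on Days 7, 14, 28 and 35 by response to treatment or reservoir elimination rate, and defines response as follows: "Response to treatment will be indicated by an absolute increase in Cycle threshold (Ct >20), or a negative rt-PCR tests results (Ct >40").

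The same item appears elsewhere in two different senses:

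- Section 2.3.2, secondary endpoints, words it as a change: "Absolute increase in Cycle threshold (Ct >20) in various treatment arms at D7, D14, D28, and D35 from baseline".
- Section 5.7(c) uses it to sort the Ct result itself, next to the cut-off for a negative test. The load is "classified as absolute increase in Cycle threshold (Ct >20), or negative rt-PCR tests results (Ct >40"). The same item notes the direction of the scale: Ct is a number "which is an inverse proportion of the parasite load".

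The phrase also stands among the secondary outcomes in section 2.3.2 and the exploratory endpoints in the synopsis and section 2.

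The primary endpoint (synopsis and section 2.3.2) follows another rule: "Proportion of people with decreased gametocyte load after treatment with" the tea, Day 35 against baseline. It sets no minimum size of decrease.

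**The concern.** A response definition should sort participants the same way whoever applies it, and should not be satisfied before treatment. Here 20 can be a difference or a level, and for the same participant the two can give opposite answers. If the choice is left until Ct values are known, the reported response rate of every regimen depends on it.

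The primary endpoint adds a further rule. Because any fall counts, ordinary assay and day-to-day variation produces apparent successes in every arm. A regimen could look effective on the primary endpoint and ineffective on the response rule, or the reverse.

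**Working it through.** **Inputs from the protocol.** The cut-offs are 20 and 40, and higher Ct means lower load. Arm sizes are in section 8.1: "Therefore 56 positive participants will be enrolled per site, making 112 participants in the whole study". They reproduce: 6 × 8 + 2 × 4 = 56 per site, and × 2 = 112. Pooled over sites, an active arm has 16 participants and a control arm 8. The protocol gives no baseline Ct distribution, no assay repeatability and no expected effect; values for these below are assumptions.

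**1. Change reading (rise of more than 20 cycles).** For baseline b, follow-up Ct must exceed b + 20. If b ≥ 20, then b + 20 ≥ 40, so only a negative result qualifies and this limb adds nobody. If b < 20 it can be met while still positive: b = 18 needs Ct > 38, and b = 15 needs Ct > 35. The fold change for 20 cycles is 2^20 = 1,048,576 at full PCR efficiency, and 1.8^20 = 127,482 at an amplification factor of 1.8.

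**2. Level reading (Ct above 20).** Any b > 20 meets it on Day 0. Ct 34 falling to 28 is a load increase of 2^(34−28) = 64-fold at full efficiency, and still counts as response. For b < 20 it is not met at baseline.

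**3. Share affected.** Assume baseline Ct is normal with SD 3 to 5 among positives (Ct ≤ 40):

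| Mean baseline Ct | Share above 20 |
|---|---|
| 18 | 25–35% |
| 20 | 50% |
| 25 | 84–95% |
| 30 | 98–100% |

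In simulated untreated participants (mean Ct 25 to 35, between-person SD 4, within-person SD 0.5 to 3), the level reading scores 84–100% as responders and the change reading about 0%.

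**4. Chance rate of the primary endpoint** (any decrease, no treatment effect):

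| Assumption | P(any decrease) |
|---|---|
| Symmetric noise, SD 0.5 to 3 cycles | 0.50–0.55 |
| Stricter selection on high baseline load | 0.54–0.64 |
| Natural decline of 0.5 to 2 cycles | 0.58–0.76 |
| Natural rise of 0.5 to 1 cycle | 0.37–0.43 |
| Only a share g = 0.3 to 0.7 carry gametocytes at baseline (0.5g) | 0.15–0.35 |

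The last row matters because the entry criterion is "Screened positive for malaria (RDT + and" qPCR positive), and gametocyte carriage is not itself required. At a 50% chance rate, an arm of 16 shows 10 or more decreases with probability 0.23.

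**5. Power, 16 versus 8, two-sided 0.05.** Assume a true shift of 3.3 cycles (log2 10 = 3.32, about a ten-fold fall) and SD s of the change.

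- Any decrease: active rate Φ(3.3/s), control rate 0.50, exact power of Fisher's test.
- Mean change: t-test with d = 3.3/s, noncentrality d × √(16 × 8/24) = 2.31d, 22 degrees of freedom. This stands in for the planned mixed model.
- Cut-off at 3.3 cycles (no negativity limb): active rate 0.50, control rate 1 − Φ(3.3/s), Fisher's test.

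| SD | Any decrease: rates | Power | Mean change: power | 3.3-cycle cut-off: rates | Power |
|---|---|---|---|---|---|
| 2 | 95% vs 50% | 67% | 95% | 50% vs 5% | 46% |
| 3 | 86% vs 50% | 39% | 68% | 50% vs 14% | 28% |
| 4 | 80% vs 50% | 23% | 45% | 50% vs 20% | 18% |

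**The case against.** The best defence is that efficacy does not rest on the 20-cycle phrase alone. The negative category (Ct above 40) is clear. Section 3 also names the reservoir elimination rate. The first secondary endpoint is the level of decrease in Ct by arm at each visit, and section 8.3 already plans a linear mixed model. The trial is a pilot with no formal sample size calculation, so low power for a single arm comparison is partly a matter of size. All of that stands. It shows that a sound analysis is within reach, but it does not make the response rule usable.

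A reader might go further and infer three things that the document does not support.

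- **That the rule can never work.** The fault is confined to baseline Ct of about 20 or more. Below that, the change reading is attainable short of a negative test and the level reading is not met at baseline.
- **That half of untreated participants will count as primary-endpoint successes.** That figure needs symmetric noise, no drift and gametocytes in everyone.
- **That no rule in the protocol can tell active tea from placebo.** Randomised controls carry the same chance rate, so any-decrease still separates the arms: 86% versus 50% at SD 3. The contrast is diluted, not biased.

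**Conclusion.** The concern holds in this form. The response rule is ambiguous between a change and a level. For baseline Ct above 20, one reading is redundant with a negative test and the other is already satisfied on Day 0, even if load later rises. This follows from the protocol's own cut-offs. The number of participants affected cannot be stated without baseline Ct.

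The primary endpoint is a separate rule with no minimum change. Its chance rate is about 50% under symmetric noise and roughly 15% to 76% across the assumptions tried. The cost is lost power and a within-arm proportion that misleads when read alone. With 16 versus 8 and an assumed 3.3-cycle shift, moving from mean change to any decrease lowers power from 95% to 67% at SD 2 and from 45% to 23% at SD 4. The effect and SDs are illustrative, since the protocol gives neither.

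**What to change.** 1. Delete the parenthesis with Ct above 20 wherever it occurs: synopsis exploratory endpoints; section 2.3.2 secondary outcomes and secondary endpoints; section 2 exploratory endpoints; section 3 Endpoints; section 5.7(c).
2. Use one definition in all these places: response is a negative rtPCR (Ct above 40), or a rise in Ct from the participant's own baseline larger than the assay's measured repeatability. Fix that value before any follow-up data are reviewed.
3. Make change in Ct from baseline versus control, in the linear mixed model already planned in section 8.3, the main efficacy comparison. Report the Day 35 proportion beside it, by arm and including the controls.
4. Do not put a 3.3-cycle cut-off on the Day 35 endpoint. If the true shift is about that size, half of treated participants would fail it, and power would fall to between 46% and 18%, below the any-decrease rule.

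The cost is a change of endpoint wording and response rates that will differ from those under the present text. No new samples or measurements are needed beyond a repeatability figure for the assay.

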Clinical symptoms (mild malaria symptoms): That may occur during the trial period will be assessed daily by site (observing) staff and recorded in the home or site visit worksheets at Visit Day 7, 14,28, and 35 including Temperature > 37°C, Chills (Perspiration), Sweats, Headaches, nausea and vomiting, body aches, general malaise (Weakness), enlarged spleen, mild jaundice, enlargement of the liver, and increased respiratory rate (>20 /min). Participants with confirmed malaria symptoms will be treated with the WHO recommended treatment for symptomatic malaria.

Data collection: Data will be captured through the Observation worksheet and entered in Electronic Case Report Forms (eCRF), by interviewing the participants during observation, reviewing available medical records, and documenting assessment records.

Written informed consent will be obtained before conducting any study related procedures or treatment on the participants. Participants will first be informed about the aim of the study, designs, potential gain, and their right to stop at any moment if they accept to enter the study. Then they will be requested to sign a written informed consent.

Ethical considerations: Administrative authorization will be obtained from the ministry of public health in Cameroon and Rwanda, and administrative authorities of the various study sites. Ethical authorization will be obtained from the Faculty of Health science Institutional Review Board (FHSIRB) of the University of Buea, Cameroon and the Rwandan National Ethical Committee (RNEC). All study participants will have a clear and detailed explanations about the study and requested to freely sign a written informed consent.

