6.2.2 Concomitant Medications and Vaccines

At each study visit, the investigator will ask the participants about any prescription or over-the counter medication(s) taken since the last visit. Any medications taken at any time during the study period must be recorded on source documents and the case report form with trade and/or generic name, indication, dose, start and end dates. Any treatments and/or medications specifically contraindicated, e.g., any investigational or nonregistered product, any antipyretic/analgesic will be checked at each study visit during treatment period. If any became applicable during the study, it would not require withdrawal of the participant from the study but may determine a participant's evaluability in the per protocol analysis.

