8.2 Analysis Populations

- **8.2.1 Enrolled Population:** All screened participants who provide informed consent and receive a participant ID, regardless of the participant's randomization and treatment status in the trial.
- **8.2.2 Exposed Population:** All participants in the enrolled population who receive a treatment dose.
- **8.2.3 Trial Populations:** Treatment trial analyses will be performed on both the Full Analysis (FA) Population and Per Protocol (PP) Population.

Full Analysis Population: All participants in the enrolled population who were randomized, received a study treatment dose, and provided an evaluable blood sample at least at one time point post-treatment. Per Protocol Population: All participants in the FA Population who correctly received all doses of study treatment per randomization with no major protocol violations that are determined to potentially interfere with the reactivity assessment of the study treatment. This population will serve as the primary analysis population for all efficacy objectives. Due to unpredictability of some irregularities, the criteria for exclusion of participants from the Per Protocol Population will be determined before the database is locked and will be based on the blind review of protocol violations.

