8.3 Analysis Plan

➤ Data management and analysis: All data will be entered into an Excel spreadsheet and then analyzed STATA 17 software packages. Descriptive statistics will be used to redistribute the treatment outcomes in the various treatment arms according to the evaluation times.

Quantitative variables will be summarized using means and medians followed by their standard deviations (SD) and Interquartile range (IQR) respectively, while qualitative variables will be summarized as percentages. Groups will be compared using a linear mixed model and trends over time will be compared using F-tests at 95% CI and statistical significance set at P < 0.05.

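### Carrying the last observed parasite load and side effects into missed visits can bias the comparison of daily and weekly schedules, and conflicts with the protocol's own safety denominators

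*Protocol*

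**What the plan says.** The rule is in the Endpoints paragraph of Protocol section 3. The sentence opens "If the patient misses the follow-up visit, compliance will be noted in the completion worksheet" and ends with "the parasite load and adverse side effects noted during the last visit considered". The wording is loose, but its natural reading is last observation carried forward (LOCF), for efficacy and side effects alike. It names no visit and no endpoint.

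These other parts of the Protocol bear on it:

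- **Primary endpoint** (section 2, Treatment endpoints): "Proportion of people with decreased gametocyte load after treatment with" the tea, judged on Day 35 against baseline. The primary objective (2.3.1) is to find the best concentration, frequency, length and formulation, which means comparing schedules.
- **Schedules** (section 3): TG1, TG2, TG4 and TG5 take the tea daily for 7 days. TG3 and TG6 take it weekly for four weeks. Follow-up visits are on Days 7, 14, 28 and 35.
- **Analysis sets** (8.2.3): the Full Analysis set needs one evaluable sample at any time after treatment. The Per Protocol set also requires correct receipt of all doses and no major violation. Of the latter the Protocol says "This population will serve as the primary analysis population for all efficacy objectives". Neither set requires a Day 35 sample.
- **Safety** (8.2.4): the denominator may differ between safety endpoints, according to who has data.
- **Model** (8.3): "Groups will be compared using a linear mixed model".

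**The concern.** A participant last seen on Day 7 can enter the Day 35 analysis with the Day 7 load. In a daily arm that value is taken at the end of the course, and carrying it forward assumes 28 days without change. In a weekly arm the same visit falls early in the course, with most doses still to come. One imputation rule therefore means different things in the arms that the trial sets out to compare.

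For side effects, a carried value can show a resolved event again at later visits, or show someone whom nobody assessed as free of events. Either distorts the by-visit proportions in the secondary endpoints.

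The rule is also not needed for the Ct values. A linear mixed model uses each participant's observed visits, under missing at random, without filling gaps. Filled values would enter that model as if they had been measured.

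**Working it through.** **Where the 10% comes from.** The only drop-out figure in the Protocol is 10%, in section 8.1 and the matching text in section 3 and the synopsis. It sizes screening. For Buea: 56 / 0.098 = 571.4, and 571.4 / 0.9 = 634.9, rounded up to the stated 635. The figure reproduces. Using 10% as the share missing at Day 35 is an assumption made here, so a range is shown.

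**Participants affected.** Section 8.1 gives 8 per active arm and 4 per control arm at each of two sites, hence 16 and 8 overall, and 2 × (6 × 8 + 2 × 4) = 112 in total. At 10% missing:

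- whole trial: 112 × 0.10 = 11.2
- active arm: 16 × 0.10 = 1.6
- control arm: 8 × 0.10 = 0.8

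**Shift in an arm's Day 35 proportion.** Let m be the share missing, p35 the true Day 35 proportion (taken as the same in those missing and those seen), and pL the proportion showing a decrease at the visit carried forward. The LOCF estimate is (1 - m) × p35 + m × pL, so the shift is m × (pL - p35).

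The Protocol gives no response rates. For illustration, assume p35 = 0.50 in both schedules, with pL = 0.80 just after a 7-day course and pL = 0.30 early in a weekly course.

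| m | daily: m × 0.30 | weekly: m × (-0.20) | false gap |
|---|---|---|---|
| 5% | +1.5 points | -1 point | 2.5 points |
| 10% | +3 points | -2 points | 5 points |
| 20% | +6 points | -4 points | 10 points |
| 30% | +9 points | -6 points | 15 points |

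If pL lay below p35 in the daily arms, their shift would be negative. The signs above follow from the assumptions, not from the Protocol.

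**Ceiling.** One participant is 1/16 = 6.25 points of an active arm and 1/8 = 12.5 points of a control arm. At 10% missing, an active arm could move by at most 1.6/16 = 10 points, and only if every carried value reversed the true outcome.

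**Side effects.** No arithmetic applies. Section 3 supplies a value for an unattended visit. Section 8.2.4 lets the denominator follow the data available. If section 3 is applied, a participant not assessed in an interval is counted in it. If 8.2.4 is applied, that participant is not. Both cannot govern the same table.

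**The case against.** The strongest case on the other side has four parts.

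- **The Per Protocol set is primary and requires all doses.** A weekly-arm participant lost at Day 7 will normally leave that set, and a value carried from Day 28 need not be mid-course in any arm. This stands and narrows the point. The bias arises mainly in the Full Analysis set and among people who took their doses but missed visits. It does not vanish, because 8.2.3 asks for no Day 35 sample.
- **A linear mixed model of Ct does not estimate the primary proportion.** This also stands. The model removes the need for filling only for Ct, and the Day 35 proportion needs its own rule. Counting missing as non-response is itself an imputation and can bias arms whose missingness differs.
- **Safety is already well covered.** Sections 7.1 and 7.1.2 require daily monitoring and follow-up of events to resolution or stabilization, and 8.2.4 already has the right denominator. That makes reconciliation easy, but the section 3 sentence still contradicts it.
- **This is a pilot, and a statistical analysis plan may exist.** Silence would be no fault, but the carry-forward rule is written in the Protocol and has to be changed there.

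A reader might also infer that parasite loads after rescue antimalarials are credited to the tea. The text does not say so. Section 3 says only "Participants with confirmed malaria symptoms will be treated with the WHO recommended treatment for symptomatic malaria". Section 6.4 allows withdrawal after an excluded medication. Section 6.2.2 says that contraindicated medication "may determine a participant's evaluability in the per protocol analysis", without naming antimalarials among its examples, and 8.2.3 leaves Per Protocol exclusions to a blind review before database lock. How these loads are handled is therefore left open. Nor is a direction established: the literature review credits artemisinin-based drugs with gametocytocidal activity, but also reports gametocytes persisting after successful therapy and potentiated transmission after artemisinin combinations.

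**Conclusion.** The point holds as a stated rule that can bias results, not as a demonstrated bias. Section 3 specifies LOCF without limit. It can distort the comparison of daily with weekly schedules, and its side-effect half contradicts section 8.2.4.

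Under the illustrative response rates and an assumed 10% missing, the effect is 2 to 3 points per arm and a 5-point false gap between schedules. The gap would be 2.5 points at 5% missing and 15 points at 30%. The true size depends on missingness and response by arm, which the Protocol does not give. The 10 and 12.5 point figures are, respectively, a ceiling and the weight of a single control participant. Neither is an expected shift.

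It is tempting to conclude that LOCF favours the short regimens. That requires loads to rise again after Day 7. The Protocol's own account of gametocytes persisting after treatment leaves the opposite possible: a Day 7 value may understate later decline in the daily arms too.

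**What to change.** In the Endpoints paragraph of section 3, delete the carry-forward rule, and add to section 8.3:

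1. **Ct values:** analyse observed values in the linear mixed model without filling, and state the missing-at-random assumption.
2. **Day 35 proportion:** carry no value forward. Name one rule in advance, for example missing counted as non-response, with an observed-case analysis as sensitivity.
3. **Side effects:** report them only for intervals actually assessed, with the number assessed as denominator, as section 8.2.4 already allows.

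The cost is a few sentences. Clinical management is unchanged. Success proportions may be stated slightly lower: with 10% missing and a true proportion of 0.50, non-response imputation gives 0.90 × 0.50 = 0.45. That 5-point fall is the same in arms with equal missingness and response, so it creates no gap between such schedules. Where missingness differs by arm it would, which is why the sensitivity analysis is needed. The observed-case analysis rests on fewer participants (16 - 1.6 = 14.4 per active arm on average at 10% missing), so its intervals are slightly wider.
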